C-Pulse® System European Multicenter Study

CLINICAL PROTOCOL (Clinical Investigation Plan)

Clinical Investigation Number: 2012-01

Protocol Change Status	
Protocol Revision #	Effective Date
PRO-04654 Revision C	13 Jan 2014

Sponsor
Sunshine Heart, Inc.
[name]
[name]
USA

CONFIDENTIAL AND PROPRIETARY DATA: This document and the information contained herein may not be reproduced, used or disclosed without written permission from Sunshine Heart, Inc.

STATEMENT OF COMPLIANCE

The C-Pulse® System Study will be conducted in accordance with the Declaration of Helsinki and EN ISO 14155:2011 (Clinical investigation of medical devices for human subjects - Good Clinical Practices.) and any additional provisions outlined in the Study Agreement. In addition, the Study will comply with any applicable European or regional regulations.

The clinical investigation shall not begin until the required approval/favorable opinion from the local Ethics Committee (EC) or regulatory authority has been obtained, as appropriate.

SIGNATURES

Site Principal Investigator

I have read and understand the contents of the C-Pulse® System European Multicenter Study protocol. I agree to conduct this study according to the requirements of the study protocol and in accordance with Good Clinical Practice and applicable regulations. I agree to supervise all Co-investigators at my site as well as the use of all devices and study materials at my institution and to ensure appropriate informed consent is obtained from all subjects prior to inclusion in this study. I agree to hold all information related to the study in confidence and not to disclose it to any third parties for a period of five years from the date of this agreement, or until this information becomes a matter of public knowledge or until a formal agreement for that purpose is entered into by the parties.

Name

[figure not shown]
Signature

Date

STUDY SYNOPSIS

Title	C-Pulse® System European Multicenter Study
Study design	Multi-center, prospective, open label study.
Study objective	The study is designed to observe the clinical outcomes of heart failure patients treated with C-Pulse® System in the usual manner and according to the approved indications and contraindications.
Enrollment	Up to 50 patients with moderate to severe heart failure who receive the C-Pulse® System will be followed up for 5 years to collect performance and safety data.
Locations	A maximum of 15 European sites will participate. Study data from additional geographies may be included.
Estimated Time Course	First Patient In: May 2013 Last Patient In: Dec 2014 Last Patient Out: Dec 2019
Introduction	Pharmacological and device-based therapies for heart failure continue to be refined though still pose challenges. Now Sunshine Heart introduces the C-Pulse® System, designed to provide the well-known clinical benefits of counter-pulsation heart pumping support while allowing the patient to move and go back home, having a quite normal day-life style.
Technology	Sunshine Heart's C-Pulse® System is a new approach for patients with moderate to severe heart failure that can be used in combination with other heart failure therapies. The device is designed to assist the heart's function, not replace it and may be implanted using a minimally invasive approach. The C-Pulse® system is designed to provide an effective, low risk and low cost wearable mechanical heart assist device for use in patients in NYHA Class III-IV ambulatory. It is intended for use in hospital and at home.

Implantable C-Pulse Cuff.

External wearable components.

How does C-Pulse® System work?	
The C-Pulse® implanted cuff is wrapped around the ascending aorta and is pneumatically driven, via a percutaneous line, by an external driver. Inflation and deflation are timed from the ECG, sensed via an epicardial lead that is connected to the percutaneous interface lead.
 
The C-Pulse® System is simple to implant and accommodates aortic anatomic variability. C-Pulse® System allows patient mobility and can be turned off or used intermittently if recovery occurs or for day-life exigencies. In addition, the C-Pulse cuff sits outside the bloodstream, therefore eliminating the need for anti-clotting medications.

Regulatory status	CE marked
Study objective	Evaluation of the post-market clinical performance and safety of the C-Pulse® System for the treatment of Heart Failure in the population of patients who meet the approved clinical conditions provided in the indications and contraindications.
Patient population	A patient population of up to 50 patients with moderate to severe heart failure refractory to optimal medical therapy, who are implanted with the C-Pulse System as clinically appropriate, will be enrolled into the Study.
Inclusion Criteria	
According to the CE mark authorization, patients with the following conditions can be included:
 
• Patient is 18 years or older• Patients with moderate to severe ambulatory heart failure [American College of Cardiology/American Heart Association (ACC/AHA) Stage C; NYHA Class III/IV ambulatory], who are refractory to optimal medical therapy.• Patients who are non-responders to CRT pacemaker therapy• Patient has signed and dated the investigation informed consent form.
Exclusion Criteria	
According to the CE mark authorization, patients with the following conditions (contraindications) have to be excluded:
 
• Evidence of significant ascending aortic calcification on postero-anterior chest X-ray or CT scan• Moderate or severe atherosclerotic aortic disease• Ascending aorto-coronary artery bypass grafts• Any history of aortic dissection• Connective tissue disorder such as Marfans disease• Previous aortic root replacement• Aorta not conforming to specified dimensional constraints• Patient has severe mitral valve incompetence, grade 4+• Patient has moderate to severe aortic valve incompetence, grade 2 - 4+• Patient has systolic blood pressure less than 90 or greater than 140mmHg• Presence of active systemic infection• Presence of bleeding or coagulation disorder (relative)

Screening process	
Patients diagnosed with moderate to severe heart failure and who are treated at the participating centers are eligible for screening evaluation. The investigator(s) will obtain informed consent for study participation from each patient prior to implementation of screening procedures.
 
Patients eligible for device implantation must meet all the inclusion and not meet the exclusion criteria (indications and contraindications based on device CE mark authorization and Instructions for Use). In addition, a screening process will be carried out with the objective of selecting ideal candidates for the C-Pulse System. Patients' suitability will be evaluated in agreement between the Investigator and Sponsor, based on the assessment of heart failure severity, concomitant cardiac disease, need for concomitant cardiac surgery, co-morbidity, life expectancy < 2 years, pregnancy and other conditions potentially interfering with the ability to manage the C-Pulse therapy.
 
As the C-pulse implantation procedure is clinically indicated patients may be enrolled prospectively with informed consent obtained prior to the procedure or retrospectively with informed consent for the collection of the patient's data obtained after the procedure as appropriate for an observational study.

Implantation procedure	
The C-Pulse Cuff and the Sense Lead are implanted through a chest incision and without the use of cardiopulmonary bypass. Only a small pericardiotomy is required, limiting the potential for bleeding and for post-operative adhesions. The ascending aorta is isolated and its circumference measured. The circumferential length is noted on the pre-marked wrap. The Cuff is passed around the aorta such that the inflating aspect of the Cuff is positioned on the outside curvature. The Cuff is then checked to fit the aorta conformably and that the circumferential marks are appropriate prior to securing of the wrap with sutures. Pre-loaded interrupted 'mattress' sutures are placed through the tail of the Cuff at the appropriate circumferential marks with the Cuff 'open', and such that the inflation chamber of the Cuff is always visualized. The sutures are then tied down and the wrap checked to be conformal to the aorta. The excess wrap fabric is trimmed off. A bipolar ECG Sense Lead is placed on the heart, most preferably the left ventricular free wall. The gas line of the Cuff is trimmed to length and it and the ECG Sense Lead are attached to the intra-corporeal "Y- connector" end of the Percutaneous Lead. The Percutaneous Lead is then tunneled beneath the rectus sheath, the extra-corporeal end of the Lead having a Patient Connector permanently attached.
 
Alternatively, the lines may be tunneled to an intermediary incision for connection, particularly if a less invasive surgical technique (sternal-sparing) is used. The Percutaneous Lead is designed to be exchanged or removed if required, the latter eliminating the exit site. If removal occurs, the Cuff and Sense Lead can remain within the thorax with the gas line of the Cuff and the connector of the Sense Lead capped off and accessible with minimal surgery in the subcutaneous tissue of the abdominal area. If the Cuff is infected, it should be removed.

Performance Endpoints	
The following performance endpoints will be assessed during follow-up visits:
 
• Improvement in INTERMACS™ and/or NYHA functional class• Freedom from worsening heart failure resulting in hospitalization, LVAD implantation, or death• Explant for recovery of ventricular function or cardiac transplantation 
Secondary endpoints assessed at 6 and 12 months post implant include:
 
• Improvement in LVEF• Improvement in Quality of Life scores• Improvement in 6MWT
Safety Endpoints	
The following primary safety endpoints will be assessed throughout each subject's participation in the investigation:
 
• All cause and device-related mortality• Aortic disruption• Exit Site infection• Internal PIL/Cuff infection• Thromboembolism• Device malfunction• All protocol-defined adverse events
Data collection	
The study will aim to collect patient data while supported with C-Pulse therapy (i.e. the subjects will be censored from analysis if the device is permanently "off" unless due to signs of recovery). Data will be captured at the following time points: Baseline, procedure, discharge assessment, clinical follow-up at 6 weeks, 6 months, 12 months, 18 months, 2 years and yearly thereafter. Data from any other additional time points may be collected and analyzed if available.
 
Data from baseline and up to 5 years of follow-up will be captured in an electronic database. Hemodynamic performance and functional testing will be determined according to procedures based on standard center practices. Any protocol-defined adverse events, including adverse device effects and outcomes will be reported by the Investigator.

Sponsor	
Sunshine Heart Inc. [name] [name] USA

Sponsor Contacts	
[name], Director of Clinical Studies [contact] Email [contact] [name], European Medical Director [contact] email: [contact]

ABBREVIATIONS

ACC	American College of Cardiology
AE	Adverse Event
AHA	American Heart Association
CABG	Coronary artery bypass grafting
CCS	Canadian Cardiovascular Society
CEC	Clinical Events Committee
CHF	Congestive Heart Failure
CI	Cardiac Index
CIP	Clinical Investigation Plan
CO	Cardiac output
CPB	Cardiopulmonary Bypass
CRF	Case Report Form
CRT	Cardiac Resynchronization Therapy
CTS	Cardiothoracic Surgeon
DMC	Data Monitoring Committee
EAB	Extra Aortic Balloon
EC	Ethics Committee

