The C-Pulse provides the patient with a treatment option avoiding or delaying the need for VAD and/or transplant procedure. The average time on the C-Pulse® device for patients is 335 days (to date) and two patients were successfully weaned from C-Pulse® within one year. Therefore, treatment with the C-Pulse® may extend the time before a patient may require a VAD or transplant, if at all.

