Observed rate of exit site infections in the C-Pulse® clinical study was 40%. However the risks associated with this type of infection are low. Normally the resolution of this type of infection is managed through use of antibiotics, antiseptics, exit site management and PIL stabilization. Since C-Pulse® is not blood contacting, the risk of sequelae, particularly sepsis, is significantly less than observed with LVADs, thus exit site infections with the C-Pulse® device are not as high a risk as in LVADs. There remains a risk of ascending infection – exit-site pain, tenderness or swelling over the subcutaneous flocking, etc., should be investigated and treated aggressively. The PIL is specifically designed as a modular component of the C-Pulse® System, such that if an infection is chronic the PIL can be removed and the infection easily treated with antibiotics.

Adoption of the requirement for a stabilization device and new infection management techniques and protocol will require the sites to treat the C-Pulse® PIL as critically as the VAD drivelines to facilitate minimizing infection. The anticipated rate of residual risk in the post-market experience following implementation of the mitigations is expected to be no greater

than 30%. This rate is acceptable since it is consistent with what is currently being experienced with other devices having a drive-line exit site.

The clinical benefit of the PIL and its design features (e.g. ease of accessibility, ability for the patient to temporarily disconnect, removability) continue to support that the benefit outweighs the residual risk.

2) Sternal wound infection

During the C-Pulse® clinical study, one patient experienced a sternal wound infection resulting from the surgical procedure. The outcome of the management of the sternal wound after several attempts for debridement and a sternal flap was an aortic disruption. The rate of this incident is low, observed at 5% (1/20).

The risks associated with this type of infection are high if not properly managed. Resolution of this type of infection is normally managed through use of antibiotics and sternal wound debridement and drainage. If the sternal wound infection progresses to include the sternal bone the Cuff should be explanted to avoid infection of the Device.

3) Pneumo-mediastinum Infection

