Another infection observed during the C-Pulse® clinical study was a pneumo-mediastinum infection that resulted from a breach in the PIL due to a patient fall. The rate of this incident is low, observed at 5%.

The risks associated with this type of infection are high if not properly managed. Resolution of this type of infection is normally managed through use of antibiotics and removal of the C-Pulse® System. Device related infections should be continuously monitored and treated accordingly to mitigate this risk (this statement is included in the C-Pulse System IFU). In addition, the revised exit site guidelines include lead stabilization techniques that will minimize trauma from falls or pulling on the exit site.

4.2. **Clinical Risk/Benefit Assessment**

The C-Pulse® uses proven balloon counter-pulsation technology to increase left ventricular coronary artery blood flow and cardiac output and to reduce the workload on the heart. The C-Pulse® System is an earlier intervention than other mechanical circulatory support therapies, such as LVADs, meeting a clinical need for relief of symptoms in heart failure patients that are refractory to optimal medical therapy and CRT therapy.

The C-Pulse® System is designed to treat clinical symptoms associated with Class III and ambulatory Class IV heart failure (INTERMACS™ category 4-7). These symptoms normally include shortness of breath, dizziness, low blood pressure and fluid retention. Patients associated with Class III and ambulatory Class IV heart failure are typically unable to engage in normal activities, compromising their quality of life.

C-Pulse® system has demonstrated patient benefits during the clinical studies to date which include the following:

- Reduction in NYHA classification by at least 1 class.
- Improvement in Quality of Life as demonstrated by MLWHF and KCCQ.
- Improvement in Ejection Fraction.
- Positive trend in 6 Minute Hall Walk capacity.
- Reductions of symptoms and the ability to be discharged and remain at home with their heart failure.

Other benefits characterize the device concept:

- C-Pulse® is designed to be implanted without the need for cardiopulmonary bypass or extensive dissection
- Device does not come in contact with blood, thus an anticoagulant therapy is not required.
- The C-Pulse® is not life-sustaining and can be disconnected as needed for personal hygiene.
- C-Pulse may be permanently stopped for patients who experience sustained left ventricular recovery.

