5.6. Schedule of Assessments

The study will aim to collect patient data while supported with C-Pulse therapy (i.e. the subjects will be censored from analysis if the device is permanently "off"). Data will be captured at the following time points: Baseline, procedure, discharge assessment, clinical follow-up at 6 weeks, 6 months, 12 months, 18 months, 2 years and yearly thereafter. Data from any other additional time points may be collected and analyzed if available.

The treatment procedure will be performed according to the instructions outlined in the current approved IFU. The data will be recorded from baseline and during a 5 year follow-up period following the enrollment. Treatments will be performed according to standard hospital practices. The clinical assessments will be done as per routine practice at the participating institutions.

The clinical variables of interest are presented in **Table 8** below. Hemodynamic performance and functional testing will be determined according to procedures based on standard center practices. Any protocol-defined adverse events, including adverse device effects and outcomes will be reported by the Investigator. All available variables of interest, that will be collected by the investigators, will also be recorded in the Study electronic CRFs.

Table 3 .Data Collection Summary.

	Pre-Implant (Baseline)	Implant	Pre-Discharge ²	6 week	6, 18 month	Annually ¹ Yr 1-5
PATIENT ELIGIBILITY	X					
GENERAL						
Demographic Data	X					
Medical History	X					
General Physical Exam	X	X	X	X	X	X
Concurrent Cardiac Meds	X	X	X	X	X	X
Weight (Height at enrollment)	X		X	X	X	X
Pregnancy test (if applicable)	X					
VITAL PARAMETERS						
Heart rate/rhythm	X		X	X	X	X
Blood pressure	X		X	X	X	X
Respiration rate	X		X	X	X	X
CARDIOPULMONARY³						
ECHO	X				X	X
6MWT	X			X	X	X
QUALITY OF LIFE						
INTERMACS™/NYHA Classification	X			X	X	X
KCCQ	X				X	X
HEMATOLOGY						
Hemoglobin	X		X		X	X
Hematocrit	X		X		X	X
Platelet count	X		X		X	X
White cell count	X		X		X	X
C-reactive Protein	X		X		X	X
BIOCHEMISTRY						
Serum sodium	X		X		X	X
Serum potassium	X		X		X	X
Serum creatinine	X		X		X	X
BUN	X		X		X	X
NTProBNP or BNP ⁴	X				X	X
Serum bilirubin	X		X		X	X
Serum ALT	X		X		X	X
Serum AST/GGT	X		X		X	X
IMPLANT DETAILS		X				
DEVICE LOG		X			X	X
DISCHARGE CHECKLIST			X			
ADVERSE EVENTS	X	X	X	X	X	X
DATA FROM THE FOLLOWING ITEMS WILL BE COLLECTED IF COMPLETED UPON PHYSICIAN REQUEST:						
MVO2	X					X
Right Heart Catheterization	X					X

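### The Synopsis and Section 5.6 censor patients at permanent device-off under different rules, and neither exempts all-cause mortality or the other safety endpoints

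*Combined protocol and SAP*

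**What the plan says.** The Synopsis (data collection) aims to gather data while patients are on C-Pulse support and adds that "the subjects will be censored from analysis if the device is permanently 'off' unless due to signs of recovery". Section 5.6 repeats the aim and says "the subjects will be censored from analysis if the device is permanently 'off", where the sentence ends without the recovery exception. Sections 6.3 to 6.5 contain no censoring rule, and no section ranks the Synopsis against the body.

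Permanent switch-off is foreseen for two kinds of reason.

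- **Recovery.** The Clinical Risk/Benefit Assessment says "C-Pulse may be permanently stopped for patients who experience sustained left ventricular recovery". Section 4.2 reports of earlier experience that "two patients were successfully weaned from C-Pulse® within one year".
- **Infection.** The Synopsis (implantation procedure) says "If the Cuff is infected, it should be removed". Section 4.3 says of a sternal wound infection reaching the bone that "the Cuff should be explanted to avoid infection of the Device".

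The Synopsis also allows the percutaneous lead to be taken out while the Cuff stays in the chest, capped off.

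On follow-up, Section 5.6 itself states "The data will be recorded from baseline and during a 5 year follow-up period following the enrollment". Section 6.2 plans five years of follow-up after implantation, and Section 7.9 treats the study as complete once every enrolled patient has been followed at five years. Section 6.4 lists all-cause and device-related mortality, aortic disruption and internal lead or Cuff infection as primary safety endpoints. Section 6.5 promises an overall mortality rate at study end.

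**The concern.** There are two separate problems. First, a patient whose device is stopped for recovery stays in the analysis under the Synopsis and is censored under Section 5.6. Second, the two rules agree on all other switch-offs, but what they agree on does not fit the safety endpoints: a death after a non-recovery switch-off is still a death from any cause, yet either rule takes it out of the analysis.

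The patients affected matter for safety. Someone whose device was stopped because of infection is unlikely to have the same outlook as someone still supported, so the censoring is plausibly informative. A patient may also be permanently off with the Cuff still around the aorta, so that a later aortic disruption or Cuff infection is a named endpoint that would not be analysed. Two analysts, each citing the protocol, could report different mortality from the same patients. Section 4.1 gives monitoring of safety and performance as the study's purpose.

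**Working it through.** No figure in the plan is contested. The sample size of 50 in Section 6.6 is used only as a denominator; its supporting table is not in the available text.

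**1. The two rules side by side**

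| Reason for permanent device-off | Synopsis | Section 5.6 |
|---|---|---|
| Recovery | stays in analysis | censored |
| Any other reason | censored | censored |

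The first row is a contradiction between sections. The second is consistent, but carries no exemption for safety.

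**2. Against the endpoint and follow-up text**

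- Section 6.5, overall mortality at study end: conflicts, because the rule applies to analysis and this is an analysis.
- Section 6.4, all-cause mortality: conflicts by the meaning of all-cause. The window is the patient's participation, so the time element conflicts only if participation outlasts device-off. Section 9.6 refers to a requirement for termination but does not define it.
- Sections 6.2 and 7.9 and the recording sentence in 5.6: follow-up to five years, not conditional on device status. The data would be collected and then not analysed.

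**3. How many patients the recovery difference could touch**

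Inputs: 2 weaned patients (Section 4.2) and a denominator of 20 (the 1/20 in Section 4.3). Assumptions: both come from the same study, weaned means permanently off, and the rate carries over.

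2/20 = 10%, exact (Clopper-Pearson) 95% interval 1.2% to 31.7%. Multiplied by 50, this is about 5 patients (0.6 to 15.8). They would contribute data until switch-off under both rules and afterwards only under the Synopsis.

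**4. A bound that needs no event rates**

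Let d deaths be counted and k of 50 implanted patients be censored alive at a non-recovery switch-off, with no other losses. Five-year mortality then lies between d/50 and (d + k)/50, so the undetermined width is k/50:

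- k = 1: 1/50 = 2.0 percentage points
- k = 3: 3/50 = 6.0 points
- k = 5: 5/50 = 10.0 points

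The values of k are assumed; the documents give none.

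**5. Whether a direction follows**

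Take constant hazards, all assumed: death on device h = 0.10 per year, non-recovery switch-off c = 0.10 per year, death after switch-off h2, horizon T = 5 years.

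- Time-to-event estimate censored at switch-off: 1 − exp(−hT) = 1 − exp(−0.5) = 39.3%.
- Deaths on device: h/(h + c) × [1 − exp(−(h + c)T)] = 0.5 × [1 − exp(−1)] = 31.6%.
- Deaths after switch-off: the integral from 0 to T of c·exp(−(h + c)t)·[1 − exp(−h2(T − t))].

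| h2 | Deaths after switch-off | True 5-year mortality | Censored estimate |
|---|---|---|---|
| 0.05 | 4.2% | 31.6 + 4.2 = 35.8% | 39.3% |
| 0.10 | 7.7% | 31.6 + 7.7 = 39.3% | 39.3% |
| 0.20 | 13.2% | 31.6 + 13.2 = 44.8% | 39.3% |

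The censored estimate is too low, right or too high according to the hazard after switch-off. A simple count of on-device deaths over 50 can only miss deaths: at h2 = 0.10 it counts 50 × 0.316 = 15.8 of 50 × 0.393 = 19.7. The plan names no estimator, so neither result can be taken as the one it would report.

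**The case against.** The strongest reply is that the rule censors patients from analysis, not from follow-up. A patient can be followed and reported and still be censored in one analysis. That stands for adverse event reporting in 8.1, death and explant reports in 8.3 and the final report in 7.10; none of these contradicts the rule. It does not help with the mortality rate in 6.5, which is itself an analysis.

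Some further points stand and limit the finding.

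- A while-supported analysis is a legitimate aim for performance.
- A reader might infer that every safety endpoint should run to five years regardless of device status. The documents do not support that. Removing the percutaneous lead eliminates the exit site, so continuing to count such patients would dilute exit-site infection and malfunction rates. An LVAD or transplant may follow, and events on those would be mixed into C-Pulse results.
- The study is single-arm and descriptive, with no hypothesis test. The contents page lists a section on earlier clinical results that is absent from the available text and may hold relevant rates.

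The sentence "Data from any other additional time points may be collected and analyzed if available" does not settle the matter for either side: it follows the list of visits, concerns timing rather than device status, and is permissive. Nor is there a real contradiction between the five-year follow-up of 6.2 and the up-to-five-year wording of 5.1, since patients die or withdraw.

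**Conclusion.** The plan is wrong as written on this point. Two sections state different censoring rules, none says which governs, and both rules, applied as worded, remove post-switch-off deaths from an endpoint defined as all-cause. This is a stated rule in conflict with the plan's own endpoint, not missing detail. Confidence is high on the text.

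A reader might infer that mortality will be understated. The documents do not show that: they give no switch-off or death rates for this study and no time-to-event method, and the direction depends on the hazard after switch-off. A reader might also infer that exclusion of later deaths is a settled decision; Sections 6.2, 6.5 and 7.9 point the other way.

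What can be said about size is the bound of 2.0 percentage points of five-year mortality per patient censored alive, assuming 50 implanted patients and no other losses. The figure of about 5 of 50 affected by the recovery difference rests on the assumptions in the working and has a very wide interval.

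**What to change.** Replace the sentences in the Synopsis and Section 5.6 with one rule, and carry it into Sections 6.3 to 6.5:

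- Make one statement on how recovery switch-offs are handled.
- Limit while-supported censoring to the performance endpoints, as a labelled analysis.
- Analyse all-cause mortality in all implanted patients to death, withdrawal of consent or five years, whichever comes first, regardless of device status.
- Count device-related mortality, aortic disruption and internal Cuff infection after device-off as well.
- Report exit-site infection and device malfunction over the time the relevant component is in place.
- Report events after LVAD implantation or transplantation separately.
- State that LVAD implantation, transplantation or explant for recovery coinciding with device-off counts as the event, not as censoring.
- Record the date and reason of permanent device-off, including device-off without explant.

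The wording costs little. The reason for an explant is already determined under 8.3.2, and Table 3 already has a device log. The real cost is vital-status and event collection after device-off, which is work for sites relying on routine practice but falls within the five years already planned. Some rates may look less favourable.
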